11.0 Specimen Collection and Banking (if applicable)

N/A

12.0 Data Management

With regard to data safety issues, PI [name] and the research team will work together to support electronic data security. Questionnaire data will be collected via REDCap survey software, which is maintained by the South Carolina Clinical and Translational Research (SCTR) Institute, an NIH Clinical and Translational Science Award (CTSA) program. SCTR has extensive experience safeguarding the security and integrity of sensitive materials, including protected health information and sensitive financial information. The secure servers that will house the data files collected from the web applications on the smartphones and web usability assessments are located at MUSC in SSL (Secure Sockets Layer) 128-bit encrypted servers behind firewalls. After each stage of the study, SCTR will provide the PI data sets for the self-report questionnaires. Respondent confidentiality will be masked in all data files by the use of project

identification numbers rather than personal information. The personal information will be linked to the project identification numbers in one file. Electronic records, including digital recordings of sessions and the file with the linked information will be maintained in password-protected locations on the secure server. All paper records will be coded with the project identification number and maintained in a locked file cabinet on a secure floor. The only document linking participants with identification numbers will be retained in an encrypted file on the secure server with access limited to the PI and research team (Drs. [name], [name], and [name]). Data presented at professional meetings or published in journals or books will not allow identification of individual participants. These procedures are expected to minimize any potential adverse effects from participating in this study.

All project staff will be required to sign a statement of confidentiality when hired. They will also be trained to obtain informed consent and provide information regarding confidentiality in the same manner, and to address confidentiality issues as they may arise in the course of interviews, assessment, or intervention. Project staff will have access to research data only for the purposes detailed in the proposal and to the extent that they need such access to fulfill their responsibilities. No information about a participant will be released to third parties (i.e., outside agencies) without written consent from participants.

All raw data will be stored in rooms that have restricted access during the day and are locked during non-working hours. All computer data will be password-protected and identified by code numbers rather than family or staff names. All data and participant records will be entered, edited, and maintained in a locked file cabinet in locked offices at the National Crime Victims Research and Treatment Center (NCVC) at the Medical University of South Carolina (MUSC). These rooms have restricted access during the day and are locked during non-working hours. These rooms are equipped with computers that have all necessary data management software. To ensure completeness and high quality of all data files, data entry personnel will always work in pairs to verify each other's work, and their work will be regularly checked by PI [name]. Descriptive analyses will always include the computation of summary means, standard deviations, and ranges that will be checked to ensure that the results are in keeping with the properties of the measures and to flag and correct invalid entries when found. Once entered and verified for accuracy, data will be backed-up on encrypted hard drives and all data shredded and recycled. This will be done by placing data booklets in specially-designated, locked containers designed for the management of all University confidential data.

Research records of individual participants will be identified by code rather than by participant name or other identifying information (e.g., address, phone number, date of birth, social security number). PI [name] will keep a master file containing the names and addresses of participants who are willing to be contacted for the purpose of the follow-up assessments. This master file will be kept in a different room from the data entry rooms. It will be stored in a locked filing cabinet in a room that will itself be locked whenever it is not being used by PI [name]. The master file will be destroyed at the end of the study (two years following the end of the last assessment), at which point there will be no way to link names to participants' data code numbers. Data presented at professional meetings or published in journals or books will not allow identification of individual participants.

Interviews will be recorded and saved under the project identification number. All audio recordings from interviews and sessions will be stored in a secure file on the PI's computer. Audio recordings will be transcribed by a professional transcription service and will be coded by the PI and Project Coordinator. Coders and the PI will have access to this data only when coding the information; audio recordings will be destroyed once the coding process is complete.

Data Analytic Plan

This study is an RCT pilot study to examine feasibility and estimate efficacy of the BWCW program for teacher stress reduction. We will randomize 12 ECEs with 12 participants/site to the BWCW and WLC arms (24 ECE sites and 288 participants). Aim 1 will (1a) evaluate the feasibility and implementation of the BWCW program and (1b) estimate treatment response and variability at 6 months. Feasibility in Aim 1a will be evaluated in the 144 participants randomized to ECEs where the BWCW program is implemented. A sample size of 144 for 1a allows us to estimate a two-sided 95% confidence interval for all feasibility outcomes with a width no larger than 0.17 and 0.24 respectively. If the lower end of the confidence interval for any feasibility outcome is smaller than 0.5 we will deem the study infeasible. For Aim 1b, participant reported stress in both groups will be evaluated at baseline and 6 months using a validated survey instrument and treatment effect will be estimated as the difference between the BWCW and controls in change in stress from baseline to post-BWCW and 6-month follow-up. The model in 1b will include a fixed effect for treatment group and a random site effect to account for clustering within ECE site. We anticipate approximately 10% loss to follow-up in both study arms and aims at post-BWCW and 6month follow-up yielding an expected sample size of approximately 129 participants in each arm at 6month follow-up for Aim 1b. It is also expected that treatment response among participants at the same site will be correlated. Assuming a conservative interclass correlation between participants at the same site of $\rho = 0.2$, the effective sample size for each treatment arm is 40 for 1a. For 1b this sample size allows us to estimate a two-sided 95% confidence interval with a distance from the difference in means to within 0.45 standard deviations. The estimated confidence interval widths are conservative as the within site correlation will likely be smaller than 0.2. Most importantly, the results from this pilot study will provide valuable information for planning a future definitive cluster randomized trial of BWCW.

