10.0 Study Design / Methods

The pilot RCT follows a 2 (treatment type) x 3 (time points) study design, in which 24 ECE centers will be randomly assigned to: (1) BWCW or (2) wait-list control (WLC), resulting in a cluster randomized trial. Using centers as the unit of assignment will reduce risk of intervention contamination among teachers. Centers will be recruited in four "waves" of six and randomly assigned to condition (3 BWCW and 3 WLC in each wave). Similar designs have been used to demonstrate efficacy of programs through RCT designs. 70,71

Pre-BWCW, post-BWCW, and 6-month follow-up surveys will be given to each participant. Surveys are completed online by participants via survey link sent to the participant.

Cortisol samples will be collected from 20 participants at baseline and 6-month follow-up time points. The samples will be collected by the participant and placed in a small cooler that a study team member will pick up from the center.

Qualitative interviews will be conducted with 30 participants enrolled in the study. Random selection for ECE teacher qualitative interviews occur through a parallel subgroup sampling procedure⁷² using random sampling conducted by wave. All participants within each wave will be assigned a number. Using a random number generator, 7-8 participants per wave will be randomly selected to participate in a qualitative interview. Participants will be recruited using this procedure until the target sample is reached (n=15 BWCW, n=15 WLC). The qualitative interviews will be audio recorded and stored on the study Box drive. Recordings will be transcribed using VerbalLink and audio tapes will be destroyed. The transcribed interviews will be labeled with the participant ID and will be stored on the Box drive.

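### The 0.17 maximum interval width for the Aim 1a feasibility outcomes ignores clustering by center; at the plan's own ICC of 0.2 it is about 0.3, and 0.24 has no stated inputs

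*Combined protocol and SAP*

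**What the plan says.** Section 10.0 assigns whole centers to condition, "resulting in a cluster randomized trial". The Data Analytic Plan at the end of section 12.0 has 12 centers of 12 teachers per arm and evaluates feasibility (Aim 1a) in the 144 BWCW teachers. That sample size, it says, "allows us to estimate a two-sided 95% confidence interval for all feasibility outcomes with a width no larger than 0.17 and 0.24 respectively". The decision rule follows: "If the lower end of the confidence interval for any feasibility outcome is smaller than 0.5 we will deem the study infeasible".

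Clustering comes in later in the paragraph. "It is also expected that treatment response among participants at the same site will be correlated", the plan says, and with an ICC of 0.2 "the effective sample size for each treatment arm is 40 for 1a". It also says: "We anticipate approximately 10% loss to follow-up in both study arms and aims". The only analysis provision for clustering is for Aim 1b: "The model in 1b will include a fixed effect for treatment group and a random site effect to account for clustering within ECE site". The closing claim covers all the widths: "The estimated confidence interval widths are conservative as the within site correlation will likely be smaller than 0.2".

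The paragraph does not give the proportion, ICC or interval method behind 0.17 and 0.24, does not say what the two figures respectively refer to, and does not list the feasibility outcomes or say whether each is measured per teacher or per center.

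**The concern.** A bound on width has to hold at the least favourable proportion, 0.5. For 144 teachers in 12 centers, 0.17 looks too small at any appreciable within-center correlation, and the paragraph itself assumes 0.2. The claim that the widths are conservative would then be untrue of this figure.

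A decision depends on it. The study is called infeasible if any lower limit falls below 0.5. If the interval used is the ordinary binomial one that reproduces 0.17, its lower limit will be too high whenever teachers in the same center respond alike, and a program of doubtful feasibility could pass. The pilot's stated purpose is to plan a definitive cluster trial, so its precision and its feasibility rule should both reflect the clustering.

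**Working it through.** **Inputs (Data Analytic Plan, section 12.0).** 144 teachers in 12 centers of 12; two-sided 95% interval; ICC 0.2; effective n of 40 labelled 1a; about 10% loss, leaving 129 per arm. Assumption: the ICC of 0.2 applies to teacher-level feasibility outcomes, as the label 1a implies.

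**Formulas.** Wald full width = 2 × 1.96 × √(p(1−p)/n), which is 1.96/√n at p = 0.5. Exact means Clopper-Pearson. Design effect = 1 + (m − 1) × ICC, with m teachers per center; effective n = n / design effect.

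**Reproducing 0.17.** With n = 144 independent: Wald 1.96/12 = 0.163; exact 0.169. Both round to or lie within 0.17.

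**Allowing for centers at ICC 0.2, p = 0.5**

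| Case | Effective n | Wald | Exact |
|---|---|---|---|
| No loss | 144 / (1 + 11 × 0.2) = 144/3.2 = 45 | 0.292 | 0.305 |
| 10% loss, 10.75 per center | 129 / (1 + 9.75 × 0.2) = 129/2.95 = 43.7 | 0.296 | 0.310 |
| Plan's own figure | 40 | 0.310 | 0.324 |

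The printed 0.17 is 56–58% of the no-loss width (0.17/0.305 to 0.17/0.292) and 55–57% of the width after loss. A t interval (11 df) on the 12 center proportions has a mean width of 0.324 with no loss and 0.328 with 10% loss.

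**Other ICCs, 144 teachers, p = 0.5**

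| ICC | Effective n | Wald | Exact |
|---|---|---|---|
| 0.02 | 118.0 | 0.180 | 0.187 |
| 0.05 | 92.9 | 0.203 | 0.211 |
| 0.10 | 68.6 | 0.237 | 0.247 |

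A Wald width of 0.17 needs n = (1.96/0.17)² = 132.9, a design effect of 144/132.9 = 1.083 and hence an ICC of 0.083/11 ≈ 0.008. The exact interval gives 0.0013. With 10% loss, 0.17 is exceeded even at ICC 0: 0.173 Wald and 0.179 exact at n = 129.

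**The 0.24.** At p = 0.5 it would need an ICC of about 0.09 (exact) to 0.105 (Wald). At effective n 45 or 40 it would need a proportion of 0.785 or 0.816 (Wald). An exact interval on 72 independent teachers also gives 0.240. The plan states none of these.

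**Aim 1b for comparison.** 1.96 × √(2/40) = 0.438, or 0.445 with t on 78 df, so the stated 0.45 SD does use the clustered effective n.

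**The 0.5 rule.** The smallest observed proportion that passes is 0.581 (Wald) or 0.585 (exact) at n = 144; 0.640 or 0.656 at effective n 45; 0.648 or 0.667 at 40.

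To see the effect of an unadjusted interval, one teacher-level outcome was simulated from a beta-binomial model (12 centers of 12, 200,000 replicates). At true proportion 0.5:

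| ICC | Coverage, Wald / exact | Pass rate, Wald / exact |
|---|---|---|
| 0.02 | 92% / 94% | 4% / 3% |
| 0.05 | 88% / 91% | 6% / 5% |
| 0.10 | 81% / 85% | 9% / 8% |
| 0.20 | 71% / 75% | 14% / 12% |

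A center-level t interval covers about 95% and passes about 2.5% in every row. Away from 0.5, the pass rates for unadjusted intervals (exact to Wald) against the center-level t interval are:

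- ICC 0.2, true 0.6: 58–61% against 24%
- ICC 0.2, true 0.7: 95–96% against 72%
- ICC 0.2, true 0.8: 99.9% against 97.6%
- ICC 0.05, true 0.6: 61–66% against 43%

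Two outcomes that must both pass, each at true 0.5 and ICC 0.2, would do so under Wald between 0.143² = 2% (independent) and 14% (perfectly correlated) of the time.

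**The case against.** The strongest objection is that 0.17 may be a half-width. At effective n 40 the half-width is 0.155 (Wald) or 0.162 (exact), so 0.17 could already include clustering, and the closing sentence does use the word widths loosely enough to take in the 1b half-width. This reading is less likely: the sentence says width, ties it to the sample of 144, and describes the 1b half-width in different terms. It also leaves 0.24 unexplained, since that half-width would need an effective n of about 17. The plan should still say which is meant.

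Second, the ICC of 0.2 is introduced for treatment response, and the label 1a may be a slip for 1b. The figure of 40 is 129/3.2 = 40.3, and 129 is the sample size given for 1b. That is a fair point. On that reading, however, the plan makes no allowance for clustering in 1a at all, and 0.17 is too small at any ICC above about 0.008 even with no loss.

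Third, the plan nowhere says that an unadjusted interval will be used, so the pass rates are conditional. They also matter little when true proportions are high or the ICC is small: at ICC 0.05 and true 0.7, about 99% pass unadjusted against 95% with the center-level t interval. This stands, and it limits the practical consequence. It does not rescue the stated width.

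Finally, the 1b figure also depends on method: t on 22 df at effective n 40 gives 0.464. That does not affect the finding on 1a.

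**Conclusion.** The concern holds: the 1a precision statement is wrong as written. The figure 0.17 is the worst-case full width for 144 independent teachers. With the plan's centers and its ICC of 0.2, the worst case is 0.29–0.31 with no loss, 0.30–0.31 after 10% loss and 0.31–0.32 at its own effective n of 40. This rests on full width being meant and on 0.2 applying to teacher-level feasibility outcomes. If 0.2 does not apply, the size of the shortfall depends on an ICC that the plan does not give, but 0.17 is already exceeded at 0.02. The figure 0.24 cannot be traced to any stated input. The claim of conservatism fits the 1b calculation and not 0.17.

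The effect on the feasibility decision depends on an interval method that the plan leaves open. It would be material for true proportions of about 0.5 to 0.7 and minor near 0.8 or above. This should be fixed before the analysis.

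**What to change.** In the Data Analytic Plan:

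- Restate the 1a maximum width as about 0.3 at ICC 0.2 and p = 0.5, printing the ICC, teachers per center, proportion, interval method and whether full or half width is meant. The values are 0.29–0.31 with 144 teachers, 0.30–0.31 with 129, or 0.32–0.33 for a t interval on 12 centers.
- State that 0.2 is assumed for feasibility outcomes, or give the width over ICCs of 0.02 to 0.2. Correct the 1a label if 1b was meant.
- Give the inputs for 0.24 or delete it, and limit the claim of conservatism to 1b.
- List each feasibility outcome with its unit. For teacher-level outcomes, say that the interval in the 0.5 rule allows for center, for example a t interval on the 12 center proportions or a design-effect-adjusted interval. For any center-level outcome use n = 12, where the exact worst-case width is 0.58 (6/12: 0.211 to 0.789). The earlier implementation results in section 2.0 are reported per program, so such outcomes are plausible.

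The cost is wording in one paragraph, a short list and one sentence on method. The drawback is less favourable stated precision and a stricter rule: at ICC 0.2 an observed proportion of about 0.64–0.66 (up to 0.67 at effective n 40) is needed to pass, in place of 0.58–0.59, so a program with a true proportion of 0.6–0.7 would be called infeasible more often.

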The Be Well Care Well (BWCW) Program, developed by the study team (PI [name] and Co-I [name]), is a program aimed at building wellbeing in ECE teachers to reduce and buffer the effects of stress and hardship, and making them better able to meet the developing social-emotional needs of young children in their care. In 2018-2019, BWCW was implemented at 33 childcare centers in SC, in which 250 ECE teachers participated in the program aimed at building social support networks, developing stress reduction techniques, improving self-efficacy and executive functions, and facilitating access to support services. Results indicated that all teacher outcomes, including stress and physical activity, were significantly improved from pre- to post-program implementation. While this provides significant preliminary support for the efficacy of the BWCW program, a randomized clinical trial (RCT) is needed to examine the impact of BWCW compared to a control intervention.

This multi-disciplinary investigative team from the Medical University of South Carolina (MUSC) and the University of Delaware (UD) have built a strong collaborative relationship via participation in an ACCEL-sponsored research planning retreat, multiple collaborations that have grown from that meeting, including pilot data collection. Built from this foundation, we aim to evaluate the feasibility and preliminary impact of the BWCW program on ECE teacher outcomes, including teacher stress, physical activity, parent-child interactions, and nutrition. Our study will address the following specific aim and hypothesis:

Aim 1: Assess the impact of the BWCW program on teacher stress and physical activity, as measured by validated survey tools at pre-BWCW, post-BWCW, and 6-month follow-up, in 144 ECE teachers within 12 centers who receive the BWCW program compared to 144 ECE teachers within 12 centers who receive the wait-list control condition in a pilot RCT Hybrid Type 1 study. We aim to finalize the trial design for a large-scale, rigorous R01-level effectiveness-implementation Hybrid Type 1 study. Benchmarks are:

- (a) Test feasibility and implementation of the pilot RCT of the BWCW program
- (b) Obtain variability estimates of outcomes (less than 10% missing data) and initial indicators of treatment effects at post-BWCW and 6-month follow-up for the subsequent efficacy trial

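### The Aim 1b stress model leaves out the randomization wave and uses change from baseline, so its confidence interval can be wider than the design and data allow

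*Combined protocol and SAP*

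**What the plan says.** Section 10.0 (Study Design / Methods) describes a cluster-randomized trial of 24 centers. They are recruited in four waves of six and "randomly assigned to condition (3 BWCW and 3 WLC in each wave". Wave is therefore a restriction on the randomization.

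The Data Analytic Plan, at the end of section 12.0, is the only description of the Aim 1b analysis. The "treatment effect will be estimated as the difference between the BWCW and controls in change in stress from baseline to post-BWCW and 6-month follow-up". On the model it says: "The model in 1b will include a fixed effect for treatment group and a random site effect to account for clustering within ECE site". Wave is not mentioned. Baseline stress is collected in both arms but enters only through the change score.

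The same section assumes an ICC of 0.2, an effective sample size of 40 per arm and a 95% interval reaching 0.45 SD either side of the difference. It adds that the "within site correlation will likely be smaller than 0.2". Section 1.0 gives the purpose of Aim 1(b): "Obtain variability estimates of outcomes (less than 10% missing data) and initial indicators of treatment effects at post-BWCW and 6-month follow-up".

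**The concern.** Balancing the arms within wave removes wave differences from the treatment contrast. If the model has no wave term, any wave difference in mean change stays in the estimated site variance. The standard error then counts variation that the design has already removed. Stable wave differences in the level of stress cancel in a change score and do no harm; only differences in change matter.

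Analyzing change fixes the slope on baseline at 1. When follow-up correlates only moderately with baseline, that slope is too steep, and adjusting for the baseline already collected gives a tighter estimate.

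Precision and variance estimates are what this pilot is meant to deliver. An interval that is too wide weakens the first indication of effect. A site ICC that contains wave variation would inflate the design effect of a later trial that also blocks by wave.

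**Working it through.** **1. The plan's own figure.** Inputs from section 12.0: 129 teachers per arm after loss, 12 per center, ICC 0.2.

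- Design effect = 1 + 11 × 0.2 = 3.2; effective n = 129 / 3.2 = 40.3 (stated: 40).
- Half-width = t(0.975; 78 df) × √(2/40) = 0.445 (stated: 0.45). With z it is 0.438.

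The stated precision reproduces, with no wave term and no baseline covariate.

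**2. Wave, on the change-score scale (SD 1).** The wave share f of between-center variance is assumed. Let V be the variance of a center mean and σ²w = 0.2f the wave variance. With 12 per center, V = 3.2 / 12 = 0.267.

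- With wave: residual variance V − σ²w on 19 df, half-width 2.093 × √(2(V − σ²w)/12).
- Without wave: each arm has 3 centers in each of 4 waves, so wave adds 9σ²w to the sum of squares on 11 df. The expected variance is V − σ²w + (9/11)σ²w, and the half-width uses t = 2.074 on 22 df.
- At f = 50%, σ²w = 0.1. Without wave: 2.074 × √(2 × 0.2485/12) = 0.422. With wave: 2.093 × √(2 × 0.1667/12) = 0.349.

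Simulation of 40,000 trials with 11 teachers per center agrees closely (half-width without / with wave):

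| Wave share | ICC 0.2 | ICC 0.1 | ICC 0.05 | Coverage without wave, ICC 0.2 |
|---|---|---|---|---|
| 0% | 0.437 / 0.441 | 0.357 / 0.360 | 0.309 / 0.311 | 95.2% |
| 10% | 0.434 / 0.424 | 0.355 / 0.350 | 0.308 / 0.306 | 95.6% |
| 25% | 0.430 / 0.399 | 0.352 / 0.334 | 0.306 / 0.297 | 96.3% |
| 50% | 0.419 / 0.350 | 0.346 / 0.306 | 0.304 / 0.281 | 97.6% |

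With wave, coverage is 94.8% to 95.3% throughout. If waves do not differ, the wave term costs under 1% in width (2.093 / 2.074 = 1.009).

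**3. The ICC passed on, at ICC 0.2.**

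- 50% share. Without wave: 0.1818 / (0.8 + 0.1818) = 0.185. With wave: 0.1 / 0.9 = 0.111. Design effects at 12 per center: 1 + 11 × 0.185 ≈ 3.0 and 1 + 11 × 0.111 ≈ 2.2.
- 10% share: 0.197 against 0.184.

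**4. Baseline, in raw-score SDs.** With one correlation r at both levels and degrees of freedom ignored, change has variance proportional to 2(1 − r) and the adjusted analysis 1 − r². The half-width ratio is √((1 + r)/2): 0.81, 0.87 and 0.92 at r = 0.3, 0.5 and 0.7. This overstates the gain, because it ignores the degrees of freedom used.

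The proposed model (wave, individual baseline, center-mean baseline) was simulated with 20,000 trials per setting, baseline and follow-up ICC 0.2 and no wave effect. With equal center sizes it reduces to a regression of center means on 18 df.

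| Center r / teacher r | Planned change model | Proposed model | Difference |
|---|---|---|---|
| 0.3 / 0.3 | 0.518 | 0.433 | 16% narrower |
| 0.5 / 0.5 | 0.437 | 0.393 | 10% narrower |
| 0.7 / 0.7 | 0.339 | 0.324 | 4% narrower |
| 0.9 / 0.3 | 0.315 | 0.306 | 3% narrower |
| 0.95 / 0.7 | 0.211 | 0.213 | 1% wider |
| True slope exactly 1 (worst case tried) | 0.446 | 0.464 | 4% wider |

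Coverage of the proposed model is 94.5% to 95.2%. At r = 0.5 with wave shares of 10%, 25% and 50%, the half-width goes from 0.435 to 0.379, 0.429 to 0.356 and 0.420 to 0.315.

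**5. Why the center-mean term is needed.** At center r 0.9 and teacher r 0.3, a single slope on the individual baseline gives 0.342 against 0.316 for change, so it is worse than the plan. Separate individual and center-mean slopes avoid this.

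**The case against.** The strongest reply is that nothing here is an error. The estimate is unbiased, the interval errs on the safe side, no hypothesis test is stated, and the one decision rule, on feasibility, does not use this model. That stands, and it limits the weight of the point.

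The gains also rest on unknown inputs. All centers come from one region (sections 7.0 and 8.0), the plan expects an ICC below 0.2, and at a 10% wave share the benefit is negligible. For baseline, a further simulation found the proposed model about 1.5% narrower at r = 0.8, in 51% of trials, with no gain at r = 0.85. This also stands. On the other side, section 3.0 allows the program to run 6 to 12 months with activities chosen by each center, so wave differences in change are plausible, though not shown.

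On the ICC, 24 centers of 11 give an estimate with SD about 0.067 at a true value of 0.2. The 10%-share shift (0.013) is about a fifth of that, and the 50%-share shift (0.074) about one SD. The error would enlarge the next trial, and nothing says that trial will be blocked by wave. This is a reason to report the ICC both ways, not to leave wave out.

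Finally, the list of model terms may not be exhaustive, and the dependent variable is not named. A longitudinal model with a common baseline mean also estimates a difference in change without fixing the slope. If that is meant, the plan does not say so, and wave is still missing.

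**Conclusion.** The point holds as a loss of efficiency, not a bias, and should be addressed in the analysis plan. The model as written does not credit the balance within wave, and on its natural reading it fixes the baseline slope at 1.

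At ICC 0.2, adding wave narrows the interval by about 2%, 7% and 16% for wave shares of 10%, 25% and 50%; at ICC 0.05 and a 50% share the gain is about 8%. With no wave effect, baseline and wave together range from 16% narrower (r = 0.3) to 4% wider (true slope exactly 1). The ICC consequence arises only if waves differ in mean change.

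These figures assume 24 equal centers of 11, the stated correlations and wave shares, and center-level degrees of freedom. Section 6.0 gives 12 teachers per center only as an average, so unequal sizes will shift them somewhat. The 0.45 SD in the plan is not an arithmetic error.

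**What to change.** For each follow-up (post-BWCW and 6 months), specify a linear mixed model of the stress score with:

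- fixed effects for treatment, wave (four levels), individual baseline stress and center-mean baseline stress;
- a random center effect;
- Kenward-Roger or Satterthwaite degrees of freedom (about 18 at center level).

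Report the treatment difference with its 95% interval and the center ICC from this model. Report the ICC without wave and baseline as well, with its uncertainty, so that the next trial can use the one that matches its design. If both follow-ups go into one model, add time, treatment-by-time, participant and center-by-time effects.

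The text should also say which stress instrument the model applies to, since Table 1 in section 4.0 lists three, and whether the center mean uses all enrolled teachers or only those followed up.

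The cost is wording only, because wave and baseline stress are already recorded. The model uses four center-level degrees of freedom (22 to 18). Wave alone costs under 1% in half-width if waves do not differ; the full model cost about 4% in the worst case tried.

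### The Aim 1b effect is defined at two follow-ups, but the plan names one model with only treatment and site and does not say whether it is fitted jointly or once per follow-up

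*Combined protocol and SAP*

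**What the plan says.** Section 10.0 sets out the design: "The pilot RCT follows a 2 (treatment type) x 3 (time points) study design". It adds: "Pre-BWCW, post-BWCW, and 6-month follow-up surveys will be given to each participant". Each teacher can therefore supply two changes from baseline.

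Benchmark (b) in section 1.0 asks for variability estimates and for "initial indicators of treatment effects at post-BWCW and 6-month follow-up for the subsequent efficacy trial".

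The Data Analytic Plan in section 12.0 defines the effect in line with this: "treatment effect will be estimated as the difference between the BWCW and controls in change in stress from baseline to post-BWCW and 6-month follow-up". It then describes the model in one sentence: "The model in 1b will include a fixed effect for treatment group and a random site effect to account for clustering within ECE site". No time term, treatment-by-time term, teacher effect, within-teacher covariance or baseline covariate is named anywhere.

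The same paragraph also points to a single time. It introduces 1b as estimating response and variability at 6 months, and it says that "participant reported stress in both groups will be evaluated at baseline and 6 months using a validated survey instrument". The two-follow-up definition of the effect comes in the same sentence as that last statement.

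**The concern.** The model as described does not settle how two changes per teacher are handled. An analyst could put both changes in one model, or fit the model twice. The two choices give different outputs.

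With treatment as the only fixed effect, a joint fit has one treatment coefficient, so any fading between the end of the program and 6 months is averaged away. A joint fit also has no teacher term, so the similarity of a teacher's two changes is partly absorbed into the site variance.

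Both outputs feed the planning of the definitive cluster trial, which the plan names as the most important use of the results. The size of the effect at each follow-up and the between-center correlation are inputs to that trial's sample size.

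**Working it through.** **1. The plan's own figures.** Inputs from section 12.0: 12 teachers per site, ICC 0.2, and about 129 teachers per arm after 10% loss.
- Design effect = 1 + (12 - 1) x 0.2 = 3.2.
- Effective sample size = 129 / 3.2 = 40.3, which reproduces the stated 40. (144 / 3.2 = 45 does not.)
- Half-width = 1.96 x sqrt(2/40) = 0.438 SD, or 0.445 SD with t on 78 df. This reproduces 0.45.

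These figures use one observation per teacher, so they fit an analysis of one follow-up at a time.

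**2. Treatment effect from a joint fit.** In balanced data the single coefficient is the mean of the two effects. For illustrative effects of -0.5 SD post-BWCW and -0.1 SD at 6 months it is (-0.5 - 0.1)/2 = -0.30. Simulation (4,000 trials per setting, 12 sites per arm, 12 teachers per site) gave -0.296 to -0.307. A model of the 6-month change alone gave -0.094 to -0.107.

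**3. Standard error from a joint fit.** In the same simulation the model SE matched the empirical SD of the estimate (for example 0.205 and 0.205). Treatment varies only between sites, and the site term carries that variation.

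**4. Site ICC from a joint fit, stable center effects.** Take total variance 1, true ICC rho, m teachers per site, and w the correlation between a teacher's two changes within a center. The documents do not give w; 0.5 to 0.7 is assumed. (Under equal variances and equal correlations, the shared baseline alone gives 0.5.) The teacher variance is T = w(1 - rho). From the balanced ANOVA mean squares the estimated ICC has expectation rho + T/(2m - 1). With m = 11 (129/12 = 10.75), 2m - 1 = 21:

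| True ICC | w = 0.5 | w = 0.7 |
|---|---|---|
| 0.05 | 0.05 + 0.475/21 = 0.073 | 0.05 + 0.665/21 = 0.082 |
| 0.20 | 0.20 + 0.400/21 = 0.219 | 0.20 + 0.560/21 = 0.227 |

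The excess is about 0.02 to 0.03. At 12 per center, the design effect 1 + 11 x ICC goes from 1.55 to 1.80-1.90 (16% to 22%) at a true ICC of 0.05, and from 3.20 to 3.41-3.49 (7% to 9%) at 0.20. An omitted time shift lowers the joint ICC slightly.

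**5. Site ICC from a joint fit, center effects that vary over time.** Let c be the correlation of a center's effects at the two follow-ups (assumed). The expectation becomes c x rho + (1 - c) x rho x (m - 1)/(2m - 1) + T/(2m - 1).
- True ICC 0.20, c = 0.5: 0.100 + 0.100 x 10/21 + 0.400/21 = 0.167 (w = 0.5). With T = 0.560 it is 0.174 (w = 0.7). Both are too low.
- True ICC 0.20, c = 0.8: 0.160 + 0.040 x 10/21 + T/21 = 0.198 to 0.206, close to the truth.
- True ICC 0.05, c = 0.5: 0.025 + 0.025 x 10/21 + T/21 = 0.060 to 0.069, still too high.

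**6. Sampling error.** The simulated SD of a single-time ICC estimate with 24 centers is about 0.04 at a true ICC of 0.05 and about 0.07 at 0.20. Both exceed the bias.

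**7. Baseline adjustment.** At an assumed correlation of 0.5 between baseline and follow-up stress, a raw change has teacher-level variance 2(1 - 0.5) = 1, and a baseline-adjusted score has 1 - 0.5^2 = 0.75. The SD ratio is sqrt(0.75) = 0.87, a reduction of about 13%.

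**The case against.** The strongest reply is that the plan never says the two changes are stacked. The precision figures use one observation per teacher, the expected 129 per arm is given for the 6-month follow-up, and the sentence on the model can describe a form applied to each change in turn. A list of terms that a model will include need not be complete, and this is a short pilot plan. On that reading treatment plus a random site effect is adequate, both effects can be estimated and the ICC is not distorted. All of this stands. What remains is that the plan does not state this reading, and that its sentences on assessment times pull in different directions.

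A second reply is that the plan names no ICC as an output, only variability estimates, and that any bias is smaller than the noise in 24 centers. The part about noise stands. The site variance is nevertheless a natural thing to carry into a cluster trial, and the plan says that planning such a trial is the main use of the results.

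A reader might infer that ignoring the repeated measures makes the treatment SE too small. It does not in balanced data, as step 3 shows. A reader might also infer that the ICC is bound to come out too high and the next trial too large. That needs both a joint fit and center effects that are stable over time. The documents establish neither.

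**Conclusion.** The point holds as a gap in specification, not as a demonstrated error in the analysis. The plan promises an effect at two follow-ups and does not say how its one described model delivers them.

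- **If fitted jointly as written:** it cannot give the two effects that benchmark (b) asks for. That conclusion needs no numerical assumption. The ICC is not the single-time value: about 0.02 to 0.03 too high under stable center effects with w of 0.5 to 0.7, and about 0.03 too low at a true ICC of 0.20 when center effects correlate 0.5 over time. Both shifts are below the sampling SD.
- **If fitted once per follow-up:** it is valid. It gives up precision by using unadjusted change scores (about 13% in teacher-level SD under the assumed correlation of 0.5), and a teacher who misses one survey adds nothing at that time.

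The stated 40 and 0.45 SD are unaffected. The change is worth making before analysis because it costs little and helps on either reading.

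**What to change.** Replace the sentence on the 1b model with a longitudinal mixed model for stress at the two follow-ups:

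- Fixed effects: treatment, time, treatment by time, and baseline stress interacting with time.
- Random center effect allowed to differ by time, for example center plus center-by-time. A single constant center effect would understate the single-time ICC if center effects vary: in simulation a true 0.20 came out as 0.177 and 0.148 at center correlations of 0.8 and 0.5.
- Unstructured covariance for a teacher's two follow-up scores.
- Report the treatment effect with its 95% confidence interval, and the center ICC, separately at post-BWCW and at 6 months.
- Fallback if the joint model does not converge: one baseline-adjusted random-center model per follow-up.

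Also reconcile the statement that stress is evaluated at baseline and 6 months with the effect definition that covers both follow-ups.

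The cost is a paragraph of wording and slightly more model fitting. Teachers with one follow-up stay in the joint analysis under a missing-at-random assumption, which should be stated. No new data are required.
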